
## **Innovation**

Although standard methods of evaluation of program implementation are proposed in this application, this effort represents the first time a buprenorphine/naloxone (Suboxone®) treatment program will be introduced in Vietnam. Its location within an HIV treatment setting represents another important and innovative feature of the work. The project is built upon two distinct prevention strategies — 1) effective drug treatment for prevention of infection among those who begin the study as HIV negative; and 2) sustained viral suppression through the effective treatment of those who begin the project already infected. The cost of integrated drug and HIV treatment has not been well examined and this also represents a unique feature of the proposed project and will provide an opportunity to gauge the public health relevance of the program. The goal of the current project is not to compare methadone with Suboxone® but to demonstrate the feasibility of the use of both medications within an HIV treatment setting and to document the barriers and facilitators to their implementation.

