**Key inclusion criteria**

- 18 or more years of age
- Meets DSM-5 criteria for opiate use disorder
- Positive urine drug screen for heroin or other opiates
- Interested in methadone maintenance or Suboxone® treatment for opiate use disorder
- Injected heroin within past 30 days by self-report, documented by “tracks” or puncture marks
- Willingness and ability to give informed consent and otherwise participate
- Provision of adequate locator information

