WHO QOL-BREF: For assessing quality of life, the World Health Organization Quality of Life (WHOQOL)-BREF will be used. Assessments will be completed at baseline, month 3, 6, 9, and 12. The World Health Organization Quality of Life (WHOQOL) project was initiated in 1991 to develop an international cross-culturally comparable quality of life assessment instrument. It assesses the individual's perceptions in the context of their culture and value systems, and their personal goals, standards, and concerns. The WHOQOL instruments were

developed collaboratively in several centers worldwide and have been widely field-tested. The WHOQOL-BREF is a self-administered, standardized instrument used as a measure of health outcome and comprises 26 items, which measure the following broad domains: physical health, psychological health, social relationships, and environment. The WHOQOL-BREF is a shorter version of the original instrument that may be more convenient for use in large research studies or clinical trials. It has been used in international settings, including the WHO collaborative study of substitution treatment (Lawrinson et al, 2008).

Urine testing: Urine drug testing will be done using rapid test kits that test for opiates, amphetamines, methamphetamines, benzodiazepines, and cannabis. These will be purchased from an approved laboratory in Vietnam. These kits provide a rapid urine test that is done on site and produces a result within five minutes. In this study, urine testing will be done monthly, with collection days being randomly selected.

HIV Testing: At the baseline visit rapid HIV testing will be used to determine HIV status and need for care. All participants who are determined to be HIV positive (two rapid positives) will be referred directly to Go Vap HIV clinic for initial assessment. All participants who test negative will be scheduled for retesting at 6- and 12-month assessment points. The test kits to be used will be WHO tested and selected in conjunction with the HCMC MOH.

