**Data Analyses for treatment and outcomes (Aims 1 and 3):** The sample of up to 500 participants will be split between HIV+ and HIV- participants. The participants will not be assigned at random to Suboxone® or methadone. The assignments will be based on clinical evaluation, and participants with a longer history of addiction, or with higher numbers of previous treatments, or participants who may be at risk for interactions between methadone and antiretroviral medications, will be more likely to receive Suboxone®. The investigators anticipate having about 40-50% of the sample receiving one medication, and 60-50% receiving the other, so there should be adequate numbers for analyses in each treatment stratum.

The goal of the analyses for Aims 1) and 3) is to assess the influences of participant characteristics on treatment outcome, and to examine whether characteristics of good outcome differ across treatment and HIV groups. Thus, the analyses will regard treatment (SUB or METH) and HIV status (+ve or -ve) as strata. Participant characteristics, drawn from the baseline administrations of the Study Specific Questionnaire, ASI, RAB, and ICD-10 assessments, will be the explanatory variables of interest, while binary factors for treatment group and for HIV status will form four strata.

The outcomes of interest include: (1) the durations of time in treatment, and time to relapse to drug use, which will be addressed using Cox proportional hazards models and its extensions; (2) measures of psychopathology and drug or sex risk behaviors, drawn from the ASI and the RAB at the 6 and 12 month points, which will be analyzed using linear or nonlinear (e.g. logistic or ordinal) mixed effects models; (3) self-reported drug use drawn from the ASI, and monthly UDS tests, which will also be analyzed using linear or nonlinear mixed effects models; (4) overall incidence of HIV among those participants negative for HIV at baseline, which will be analyzed using a logistic regression model.

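### HIV incidence counts infections acquired just before entry as on-study infections, which modestly overstates the 0–12 month figure if incidence falls after entry

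*Combined protocol and SAP*

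**What the plan says.** In Study Procedures, the HIV Testing paragraph sets baseline status by rapid test: "At the baseline visit rapid HIV testing will be used to determine HIV status and need for care". Two rapid positives define a positive. For the rest, "All participants who test negative will be scheduled for retesting at 6- and 12-month assessment points".

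In the Analysis Plan (Data Analyses for treatment and outcomes, Aims 1 and 3), outcome (4) is "overall incidence of HIV among those participants negative for HIV at baseline, which will be analyzed using a logistic regression model". Baseline RAB measures are among the explanatory variables, and the RAB description gives its recall period as the preceding six months.

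The Key inclusion criteria require "Injected heroin within past 30 days by self-report", so recent exposure is a condition of entry.

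No section addresses the period in which an infection is present but not yet detectable. There is no early retest of negatives and no rule for positives found at month 6. Viral load is planned only for HIV-positive patients, and the tissue specimen section answers No to banking blood, so stored samples could not settle the question later.

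**The concern.** A participant infected shortly before entry can test negative at baseline, turn positive at month 6, and enter the incidence count as if infected during the study. These cases all surface in the first interval.

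Three uses of the figure are exposed:

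- **The descriptive incidence itself.** The Innovation section names "effective drug treatment for prevention of infection among those who begin the study as HIV negative" as one of the project's two prevention strategies, so readers will take the incidence figure as evidence on that, and may set it against an outside rate.
- **The predictor model.** Undetected pre-entry infections were acquired during the six months that the baseline RAB covers. They could make baseline risk look like a predictor of on-study infection.
- **The economic analysis.** It gives prevented HIV transmissions as an example outcome, although it does not say that observed seroconversions would supply that number.

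**Working it through.** The documents give no HIV incidence, test window or expected event count, so there is no figure to reproduce.

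**Inputs from the documents**
- Up to 500 participants (Design), about 40% expected to be HIV-positive: 500 × 0.60 = 300 baseline negatives.
- 12-month follow-up of about 90% (Assessments; Study Retention): 300 × 0.90 = 270.
- Tests at 0, 6 and 12 months.

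**Assumptions, not in the documents**
- Window w = 0.5, 1 or 3 months. The test kit has not been chosen.
- On-study rate divided by pre-entry rate, r = 0.4 or 0.6, with r = 1 as the no-change case. The 0.4 to 0.6 range borrows the 40–60% reduction in injection and sharing events cited in the background; it is not a figure for HIV incidence.
- Pre-entry rate L of 2, 5 or 10 per 100 person-years, with constant rates before and after entry.

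**Net overstatement.** With a window of w months, tests at 0 and 12 months capture infections acquired from −w to 12 − w months. Infections in the w months before entry are added; those in the last w months before the final test are missed. For small risks:

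- Observed ≈ L·w/12 + rL·(12 − w)/12
- True = rL
- Observed/true − 1 = w/(12r) − w/12 = (w/12)(1/r − 1)

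The rate ratio that would appear is w/12 + (1 − w/12)r. The share of month-6 positives that predate entry is w/[w + (6 − w)r].

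| w (months) | r | Net overstatement | Apparent rate ratio | Month-6 positives predating entry |
|---|---|---|---|---|
| 0.5 | 0.6 | 2.8% | 0.617 | 13% |
| 1 | 0.6 | 5.6% | 0.633 | 25% |
| 3 | 0.6 | 16.7% | 0.700 | 62.5% |
| 0.5 | 0.4 | 6.25% | 0.425 | 19% |
| 1 | 0.4 | 12.5% | 0.450 | 33% |
| 3 | 0.4 | 37.5% | 0.550 | 71% |

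Example: w = 3, r = 0.4 gives (3/12)(1/0.4 − 1) = 0.25 × 1.5 = 37.5%. Using exponential risks instead of the small-risk formula, the extremes are about 3% and 36–37%, and they barely change for L from 2 to 10 per 100 person-years. At r = 1 the net overstatement is zero for every w.

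**Counts** (n = 270, L = 5 per 100 person-years, r = 0.4). True on-study infections: 270 × (1 − exp(−0.02)) = 5.35.

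| w (months) | Pre-entry counted | Late infections missed | Observed |
|---|---|---|---|
| 0.5 | 0.56 | 0.22 | 5.68 |
| 1 | 1.12 | 0.44 | 6.01 |
| 3 | 3.35 | 1.33 | 7.32 |

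Observed is slightly below true + counted − missed because someone already infected before entry cannot be infected again. Over all assumed rates and windows, the pre-entry infections counted run from 0.22 to 6.67.

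**Months 6 to 12 alone.** Among participants negative at 6 months, the month-12 test captures infections acquired from 6 − w to 12 − w. For any w under 6 months this contains no pre-entry infection, and under constant rates a true ratio of 0.40 stays 0.40. Expected events are roughly half the total, about 2.7 in this example.

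**The case against.** The strongest reply is that the plan has no prevention effect to distort. HIV incidence is neither a primary nor a secondary outcome, there is no untreated comparator or pre-entry rate, and the stated goal of these analyses "is to assess the influences of participant characteristics on treatment outcome, and to examine whether characteristics of good outcome differ across treatment and HIV groups". That stands, and it limits the harm to a descriptive figure, the predictor model and any comparison a reader makes with an outside rate.

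A reader might go further and infer that the programme's prevention effect would be hidden. The documents do not support this: no such effect is estimated, and even against an outside rate a ratio of 0.40 would appear as 0.43 to 0.55, which is attenuation.

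A reader might also count only the pre-entry infections that are added, w/(12r). That gives about 7% to 62% over the same ranges, and 4% to 25% at r = 1. It omits the infections that the same window hides before month 12. The bias is upward only if incidence falls after entry.

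Nor does the plan say that later positives were acquired on treatment. It follows people who leave the programme as well as those who stay, so the figure is on-study incidence.

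Finally, the effect is small beside chance. At w = 1 in the example the count moves from 5.35 to 6.01, about 0.7 infections, against a Poisson standard deviation of √5.35 ≈ 2.3. This also stands. It makes the point a minor one, but it does not remove a bias whose source is known and can be shown from tests already planned.

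**Conclusion.** The point holds as a low-cost improvement. Outcome (4) has no safeguard against infections acquired just before entry, and the entry criteria make such infections plausible. If incidence falls after entry, the 0–12 month figure is overstated by about 3% to 37% net, assuming w of 0.5 to 3 months and r of 0.4 to 0.6. The upper end depends on a 3-month window that nothing in the documents supports or excludes.

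The distortion is concentrated at month 6, where about 19% to 71% of positives would predate entry at r = 0.4. The effect on the association with baseline RAB risk is a plausible direction and has not been sized.

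**What to change.** In outcome (4) of the Analysis Plan:

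1. Report seroconversions and incidence separately for entry to month 6 and for months 6 to 12 (participants negative at 6 months), beside the 0–12 month total.
2. Label the 6–12 month figure a sensitivity estimate of on-study incidence free of pre-entry infection. It should not replace the total or be called on-treatment incidence.
3. State that month-6 positives may predate the first dose, and that associations with baseline RAB risk should be read with this in mind.

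Settle this before the analysis, so that the handling of month-6 positives is not chosen after the results are seen.

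The cost is a sentence or two and an extra table row or two, with no extra test or visit. The drawback is precision: the second-interval estimate rests on roughly half the events and on people still followed at 6 months, so its confidence interval will be wider.

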**Study Retention:** A series of structured activities will be used to maximize completion of follow-up appointments. These activities are considered core principles in conducting longitudinal studies and have been shown successful in many different cultural settings. The investigators believe that with the intensive and structured efforts described below, the proposed project can achieve a 90% retention rate at 12 months. Most importantly, research staff will maintain accurate and timely follow-up contact information for all participants throughout the study. A basic philosophy of the work to be implemented is that follow-up begins when the initial relationship is established, and the data is collected at the time of recruitment and enrollment. Thus, a detailed locator interview will be completed for all subjects following completion of the informed consent at the time of enrollment. This will be updated at all subsequent contacts. All future appointments for research assessments will be scheduled on a calendar at the time of enrollment. A copy of this visit schedule will be given to the participant. Ten days prior to all scheduled assessment visit, calls reminding subjects about their scheduled assessment will be completed and a note will be left in the methadone dispensing area reminding the participant about the time and location of the assessment visit. Missed calls will be noted and attempts to contact the participant will continue until contact is achieved. For those who are not able to be contacted through the clinic or by phone, staff will visit contact locations collected from the participant at the time of enrollment and updated at their most recent contact. Reminder calls will also be made on the day before the scheduled appointment. Missed appointments will be responded to immediately. At the end of each day, the designated follow-up staff will attempt to contact all the subjects who missed their appointment that day. For those who unable to be reached by phone, a reminder letter will be sent within three days. Outreach by research staff will also be used to locate missing subjects. When unable to make contact after 5 days, research staff members will implement outreach procedures, including visiting the subject's home, contacts, and common "hangouts" reported by the subject at the time of their prior visit. Subjects who are reported to be incarcerated will have a note placed in their retention file and staff will periodically update the status of the participant through contact with the friend or family member who initially reported the incarceration.

### **Analysis Plan**

All data will be collected by research staff based at the Go Vap clinic. Trained staff will review all forms prior to the completion of the study visit to minimize problems associated with missing values and incorrect skip patterns. All assessments will be recorded on final version of the Case Reporting Forms (CRFs). CRFs will also be developed to capture the results of all biological assessments. All CRFs will be completed and stored using only participant identifying numbers and will not include names, addresses, or other data that could possibly be used to disclose the identity of the participant. All completed CRFs will be filed in locked cabinets by ID number. Consent forms, locator information, and other forms with personal identifiers will be securely stored separately. Research staff at the project site will be responsible for entering all data into the secure web-based data management system operated by the Data Management Unit of the University of Pennsylvania, Center for Studies of Addiction (CSA).

The data management and the quantitative analyses will be performed by the Center for Studies of Addiction data analyst, under the supervision of the PI and [name], the CSA Statistician. [name] will supervise the economic analyses. Prior to performing analyses, standard data screening and cleaning procedures will be applied (Tabachnik & Fidell 2001). These procedures will (1) screen the data for data-entry errors, (2) check for outliers, (3) assess the extent and pattern of missing data, and (4) check that appropriate assumptions of normality are met whenever necessary.

The planned analyses will be sharply focused on providing information able to inform the primary aims of the study.

- 1) *Establish a new integrated MAT treatment program within and HIV treatment setting in HCMC.* This aim will be fully documented by descriptive data focused on the numbers of patients treated by methadone and Suboxone. Data to summarize the duration of and response to treatment by patients in each of the four groupings—Methadone treated HIV-; Methadone treated and HIV+; Suboxone® treated and HIV-; and Suboxone® treated and HIV+ will be presented. The project's goal is not to compare treatment but to provide data to demonstrate that these treatments are producing results consistent with “clinical expectations” for these approaches and patient populations.
- 2) *Evaluate barriers and facilitators to implementation of integrated MAT/HIV treatment.* For this aim the study will carefully document the “events” or “factors” that are identified as having an influence on the ability and speed of implementation. Three stakeholder groups will be monitored—the drug using and patient population, the program staff, and the local government and non-government organizations. Data will be assembled using a monthly implementation log and formally assessed using semi-structured interview strategies.
- 3) *Evaluate patient retention and medication adherence in integrated MAT/HIV Care.* This aim will be critically important in documenting the success of implementation of the program. The study will carefully monitor through the baseline, 6- and 12-months assessments both retention in treatment and response to treatment. Retention will include measures of medication visit completion for expected methadone and Suboxone® administration visits as well as adherence to antiretroviral medication. Biological markers of these measures will also be collected. Results of monthly urinalyses for all participants will be reported and semiannual viral load measures for HIV positive patient will be summarized.
- 4) *Estimate the costs and benefits of MAT treatment strategies.* A cost-effectiveness analysis is an economic evaluation technique that may be used to evaluate multiple strategies to achieve an outcome. A cost-utility analysis is a special kind of cost-effectiveness analysis that may be used to compare strategies that affect morbidity and mortality (Gold et al. 1996; Haddix et al. 2003). One potential barrier to implementation of an enhanced intervention is the number of resources that must be devoted to administer the additional procedures. However, resource-intensive interventions may be justified through the achievement of better outcomes resulting from administering the enhanced procedures.

**Data Analyses for treatment and outcomes (Aims 1 and 3):** The sample of up to 500 participants will be split between HIV+ and HIV- participants. The participants will not be assigned at random to Suboxone® or methadone. The assignments will be based on clinical evaluation, and participants with a longer history of addiction, or with higher numbers of previous treatments, or participants who may be at risk for interactions between methadone and antiretroviral medications, will be more likely to receive Suboxone®. The investigators anticipate having about 40-50% of the sample receiving one medication, and 60-50% receiving the other, so there should be adequate numbers for analyses in each treatment stratum.

The goal of the analyses for Aims 1) and 3) is to assess the influences of participant characteristics on treatment outcome, and to examine whether characteristics of good outcome differ across treatment and HIV groups. Thus, the analyses will regard treatment (SUB or METH) and HIV status (+ve or -ve) as strata. Participant characteristics, drawn from the baseline administrations of the Study Specific Questionnaire, ASI, RAB, and ICD-10 assessments, will be the explanatory variables of interest, while binary factors for treatment group and for HIV status will form four strata.

The outcomes of interest include: (1) the durations of time in treatment, and time to relapse to drug use, which will be addressed using Cox proportional hazards models and its extensions; (2) measures of psychopathology and drug or sex risk behaviors, drawn from the ASI and the RAB at the 6 and 12 month points, which will be analyzed using linear or nonlinear (e.g. logistic or ordinal) mixed effects models; (3) self-reported drug use drawn from the ASI, and monthly UDS tests, which will also be analyzed using linear or nonlinear mixed effects models; (4) overall incidence of HIV among those participants negative for HIV at baseline, which will be analyzed using a logistic regression model.

The analyses will follow the same overall analytic strategy for each set of models. First, the participant characteristics will be examined separately. For a given characteristic, the analyses will first test for heterogeneity (interaction) between the characteristic and the stratifying variables of treatment and HIV status. Two types of heterogeneity are possible: the characteristic could have effects that differ across some combination of the treatment and HIV groups (three-way interaction) or its effects may be independent of one variable but differ across levels of the other (two-way interaction). In either of these cases, stratum-specific estimates of the effects will be reported. If no heterogeneity is detected, the adjusted (pooled) estimates of effect will be reported. In each case, the estimates on an appropriate scale (e.g., odds ratios, or regression coefficients associated with interpretable changes in the level of the participant characteristic), together with appropriate confidence intervals will be reported. Once the univariate effects of the different characteristics will be assessed, multivariate models containing what appear to be the important characteristics will be performed, and these models will be implemented and reported in the same way as for the univariate models.

**Data Analyses for Economic Outcomes (Aim 4):** Standard cost-effectiveness and cost-utility analyses will compare costs and benefits of the two approaches (Gold et al., 1996; Haddix et al., 2003). The analyses will be carried out from a societal perspective which means that all costs and benefits, regardless of who pays or incurs them, will be included.

Benefits may be considered as reductions in sex risk behaviors (e.g., condom use and decreased number of partners) and less risky drug-use practices (e.g., decreased needle sharing and works sharing) during follow-up. In addition, a measure of the quality-adjusted life-years (QALYs) of sex partners saved by the intervention versus the standard of care will be estimated. Benefits will be compared to the direct and indirect costs (i.e., lost productivity) of the intervention and standard of care procedures. Relevant costs include time for the administration of the HIV counseling and testing, HIV test kits, completion of intervention questionnaires, time of staff to collect blood and follow-up assessment data and the time of participants to complete the follow-up assessments.

Incremental cost-effectiveness ratios will be computed to find the additional net cost (costs minus benefits) per outcome (e.g., cases of HIV transmission prevented or QALY saved) by administering the behavioral intervention over standard procedures. To check the sensitivity of results, univariate and multivariate sensitivity analyses, in which parameter values in the mathematical models are varied from baseline values, will be conducted.

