**Behavioral Drug and Risk-Reduction Counseling Visits (BDRC):** At the enrollment visit, participants will be scheduled for the 12 weekly counseling sessions. Approximately every four weeks, participants will be asked to provide urine for drug testing during the counseling visits for the first year of enrollment. Women will have pregnancy testing approximately every four weeks during counseling visits. Monthly counseling sessions will be scheduled approximately every four weeks beginning at week 16 through week 52. At each of these sessions, participants will be asked to update their locator information and provide urine for drug and pregnancy testing (for women in the substitution treatment arm only). Monthly counseling sessions can also be combined with dispensing and follow-up visits.

**Implementation Research Strategy:** To assess implementation and costs, the study will collect data from the individual study participants, from the program staff, and from the PAC and MOH of HCMC. The project wants to document the extent to which the program achieves the intended goals at the individual level as well as documenting aspects of the process that facilitate implementation. The investigators will use a mixed methods approach that includes both qualitative and quantitative data collection. Direct comparison of outcomes between methadone patients and Suboxone® patients is not the purpose of this project. The project will not randomly assign patients to their treatments. In fact, the project will examine the response to treatment to look for patient characteristics that are associated with success in each modality.

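### One-characteristic estimates for the ASI and RAB follow-up scores omit the baseline value of the same score: valid as prognosis, but not on their own informative about response (minor, cheap to improve)

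*Combined protocol and SAP*

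**What the plan says.** All of the modelling text is in the Analysis Plan, under Data Analyses for treatment and outcomes (Aims 1 and 3).

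- **Outcome.** Outcome (2) is "measures of psychopathology and drug or sex risk behaviors, drawn from the ASI and the RAB at the 6 and 12 month points", analysed by linear or nonlinear mixed models. Outcome (3) includes ASI self-reported drug use, with the same class of model. Baseline is not one of the visits named for outcome (2), and no baseline covariate or change score is specified for either outcome.
- **Explanatory variables.** Participant characteristics "drawn from the baseline administrations of the Study Specific Questionnaire, ASI, RAB, and ICD-10 assessments, will be the explanatory variables of interest". Baseline ASI and RAB are therefore candidate predictors.
- **First stage.** "First, the participant characteristics will be examined separately". Each is tested for interaction with treatment and HIV status. "If no heterogeneity is detected, the adjusted (pooled) estimates of effect will be reported"; otherwise stratum-specific estimates are given. Confidence intervals are reported in either case.
- **Second stage.** "multivariate models containing what appear to be the important characteristics will be performed". Reporting at this stage follows the pattern of the first: "these models will be implemented and reported in the same way as for the univariate models".
- **Goal.** The section sets out "to assess the influences of participant characteristics on treatment outcome". The Implementation Research Strategy paragraph under Procedures says that "the project will examine the response to treatment to look for patient characteristics that are associated with success in each modality". Aims 1 and 3 in the Analysis Plan also speak of response to treatment, and Aim 3 ties it to the baseline, 6-month and 12-month assessments.

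**The concern.** A follow-up score without its starting value mixes two things: how severe the participant was at entry, and how far the participant moved. A characteristic that merely goes with high entry severity will be associated with a high follow-up score even if it says nothing about improvement.

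The term adjusted in the first stage does not help. It describes estimates pooled over the four treatment-by-HIV strata once no heterogeneity is found. Nor does it help that baseline ASI and RAB are candidates: they are examined one at a time like the rest, so they adjust nothing in the other univariate models.

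At stake is how the reported univariate estimates are read. Someone looking for characteristics linked to response could take a marker of entry severity for one. The outcomes touched are the two listed secondary ones, ASI drug use and severity and RAB risk behavior.

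**Working it through.** **No figure to reproduce.** The documents give no correlation, SD, alpha or power for these models. What follows is an illustration on stated assumptions.

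**Inputs from the documents.** Up to 500 participants (Design; Analysis Plan); 12-month follow-up of 90% (Assessments; Study Retention), so 500 × 0.9 = 450; about 40% HIV-positive (Design); 40–50% on one of the two medications (Analysis Plan).

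**Assumptions.** Two-sided alpha 0.05; standardized scores; a linear model at one visit; rho = correlation of baseline with follow-up score; c = correlation of the characteristic with the baseline score. The characteristic has no association with follow-up once the baseline score is known.

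**Formula.** The expected unadjusted slope is r = rho × c. With z = r√n / √(1 − r²), the chance of p<0.05 is Φ(z − 1.96) + Φ(−z − 1.96).

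Worked case, rho 0.5 and c 0.3: r = 0.15; z = 0.15 × 21.21 / 0.989 = 3.22; chance 0.896. The simulated columns come from 4,000 studies per row, with treatment, HIV status and their product in every model.

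| rho | c | slope (SD per SD) | formula | simulated, univariate | simulated, with baseline |
|---|---|---|---|---|---|
| 0.1 | 0.2 | 0.02 | 7.1% | 6.4% | 4.9% |
| 0.2 | 0.3 | 0.06 | 24.7% | 24.2% | 5.4% |
| 0.3 | 0.2 | 0.06 | 24.7% | 25.5% | 5.1% |
| 0.3 | 0.3 | 0.09 | 48.3% | 46.0% | 5.2% |
| 0.5 | 0.2 | 0.10 | 56.8% | 57.6% | 4.9% |
| 0.5 | 0.3 | 0.15 | 89.6% | 89.0% | 5.2% |

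At rho 0.3–0.5, adding baseline brings the mean slope to 0.00. With 360 followed, the univariate range at rho 0.3–0.5 is 21–81%. In the smallest expected stratum (500 × 0.4 × 0.4 × 0.9 = 72) the formula gives 8% at rho 0.3, c 0.2 and 25% at rho 0.5, c 0.3.

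**Direction.** The slope on change from baseline is rho × c − c. At rho 0.5 and c 0.3 this is 0.15 − 0.30 = −0.15, against +0.15 on follow-up level. The same characteristic can look unfavourable on level and favourable on change.

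**Multivariate stage.** The plan does not define important. Taking it as univariate p<0.05 (an assumption), the baseline score is selected in 99–100% of studies at rho 0.2–0.5, and the characteristic is still flagged after both stages in 2.4–3.0%. At rho 0.1, baseline is selected in 55–57% and the characteristic flagged in 3.6–4.0%.

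**Error in the baseline score.** The return to 5% assumes that the characteristic is unrelated to follow-up given the *measured* score. Suppose instead that it tracks true severity, measured with reliability L (not in the documents). The unadjusted slope is then rho × c / L, and the adjusted slope rho × c × (1/L − 1) / (1 − c²). At L = 0.7, rho 0.5 and c 0.3 these are 0.15 / 0.7 = 0.214 and 0.15 × 0.429 / 0.91 = 0.071. Adjustment removes about two-thirds (1 − 0.071/0.214 = 0.67), not all. In simulation over rho 0.3–0.5 and c 0.2–0.3, the adjusted estimate reaches p<0.05 in 8–37% at reliability 0.7, 7–17% at 0.8 and 5–7% at 0.9.

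**Precision.** In a logistic model with 40% positive, the standard error rises from 0.0980 to 0.1028 (rho 0.3, c 0.2; ratio 1.05) and from 0.0996 to 0.1118 (rho 0.5, c 0.3; ratio 1.12).

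**The case against.** The strongest reply is that the estimates answer the question asked. The section's goal is the influence of characteristics on outcome, and Overall objectives describes success largely as status at one year. The documents never define response as conditional on baseline, and they do not say that univariate estimates will be presented as predictors of response. This stands: the univariate estimates are not wrong and should be kept. It does not close the matter, because the protocol uses the language of response in three places, and Aim 3 refers it to the baseline assessment as well as the follow-up ones.

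The second reply is that the multivariate stage deals with it. Mostly it does, as the selection figures show. A reader might infer that the final models are contaminated; neither the documents nor the calculations support that. What remains is that inclusion of baseline is left to an undefined judgement, and that the univariate estimates are reported regardless.

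The third reply is that 25–89% is the chance of detecting a real marginal association. That is correct. Reading it as a false-positive rate would be a mistake. The entry rule of heroin injection in the past 30 days may also narrow the RAB injection items and push them toward the 6–24% range.

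The fourth reply is that adjustment cures less than it promises. This also stands. Error in the baseline score leaves residual association. With no randomization and no untreated group, neither estimate shows an effect of treatment.

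**Conclusion.** The point holds as a minor, inexpensive improvement. For ASI and RAB scores at 6 and 12 months and for ASI self-reported drug use, the reported one-characteristic estimates are sound as prognosis for follow-up level. Alone, they do not distinguish entry severity from response. Baseline would usually enter the multivariate models, but nothing requires it.

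The monthly urine tests in outcome (3) are outside this point; a positive opiate screen is an entry criterion, so the opiate result at entry does not vary. The primary outcomes (implementation, retention, adherence, cost-effectiveness) are not affected.

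The size is illustrative. It rests on assumed correlations (rho 0.3–0.5, c 0.2–0.3; weaker at rho 0.1–0.2), n=450 and an error-free baseline score. A reader might go further and conclude that the univariate analyses are invalid, or that baseline adjustment would reveal who benefits from treatment. The documents support neither: prognosis is a stated goal, and the design has no comparison from which a treatment effect could be isolated.

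**What to change.** In the Analysis Plan, for outcome (2) and for ASI self-reported drug use in outcome (3):

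- (a) Include the baseline value of the same score as a fixed covariate in every multivariate model.
- (b) Report a baseline-adjusted estimate beside each univariate estimate, except where the characteristic is that score or one of its items.
- (c) Label the unadjusted estimates as prognostic and the adjusted ones as associations conditional on measured entry level. Note that neither shows an effect of treatment and that error in the baseline score leaves some residual association.

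The cost is plan wording and one extra column of estimates. ASI and RAB are already collected at baseline, 6 and 12 months, and the RAB refers to the preceding six months, so its baseline value is like-for-like. The adjusted estimate leaves out effects that act through entry severity, and in logistic models its standard error is about 5–12% larger at rho 0.3–0.5. Reporting both estimates covers the first of these.
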